#### ***Medical History and Concurrent Disease Exclusions***

##### ***Cardiovascular diseases***

12. Any of the following disease within 6 months prior to Randomization Visit (V1):
  - Myocardial infarction
  - Cardiac revascularization surgery (coronary artery bypass graft / percutaneous transluminal coronary angioplasty (CABG / PTCA))
  - Unstable angina
  - Transient ischemic attack, stroke or cerebrovascular disease
13. Any history of heart failure (HF)
14. Unstable or undiagnosed arrhythmias, long QT syndrome, short QT syndrome, history of drug-induced Torsade de Pointe
15. Uncontrolled high blood pressure (BP): diastolic BP  $\geq 100$  mmHg or systolic BP  $\geq 160$  mmHg with or without antihypertensive treatment during Screening Period and/or at Randomization Visit (V1). BP measurement is the mean of 3 measurements and can be repeated once. If currently treated for hypertension: patients must be on stable therapy (i.e. same doses and same drugs) for the last 1 month prior to Randomization Visit (V1)
16. Lipid-lowering drug treatment modified (doses and/or drugs) during the past month prior to Randomization Visit (V1)

##### ***Hematological and oncological diseases***

17. Active malignancy or malignancy with a complete remission date within 2 years prior to Randomization Visit (V1) (with the exception of treated basal cell carcinoma or treated squamous cell carcinoma of the skin)
18. Any history of bladder cancer or unexplored macroscopic hematuria
19. History of haemoglobinopathies (e.g., sickle cell anemia or thalassemia, sideroblastic anemia)

##### ***Endocrinological disease***

20. Diabetes other than T2DM
21. Uncontrolled hypothyroidism (thyroid stimulating hormone (TSH)  $> 2 \times$  the upper limit of normal (ULN) during Screening Period)

##### ***Other exclusion conditions***

22. Any recent (<1 year prior to Randomization Visit (V1)) history of bone fracture
23. Postmenopausal women with a bone mineral density (BMD) T-score  $\leq -2.5$  SD (osteoporosis) measured by standard dual-energy X-ray absorptiometry (DXA) within 6 months prior to Randomization Visit (V1) or if not available, during the screening period. Postmenopausal

women with a T-score between -1 and -2.5 SD can be included if they are treated according to standards of care for osteopenia

24. Immunocompromised patients such as patients that underwent organ transplantation or are diagnosed with human immunodeficiency virus (HIV)

25. Any other known serious disease (such as major infection, clinically significant gastrointestinal disorder, major autoimmune disease) or other disease which in the Investigator's opinion would exclude the patient from the study

26. Any recent (< 5 years) or current drug addiction

27. Mental handicap, limited capacity of recognition, inability to follow the study procedures as evaluated by the Investigator, or any history of clinically important emotional and/or psychiatric illness

28. Anorexia or bulimia

29. Known hypersensitivity to any of the constituents or excipients of the investigational medicinal product (IMP) or pioglitazone, or history of relevant drug and/or food allergies (e.g. anaphylactic, anaphylactoid reactions)

30. Use of non-permitted concomitant medication within 6 months prior to Randomization Visit (V1) (*A transient intake < 2 weeks may be allowed with the approval of the Medical Monitor and the POXEL Medical Representative*):

- Any medication containing pioglitazone (e.g. Actos®, Actoplus Met®, Duetact®, Oseni®) or other approved or experimental thiazolidinediones (TZDs) (e.g. rosiglitazone (Avandia®), l eriglitazone (MIN-102), MSDC-0602K), or peroxisome proliferator-activated receptor  $\gamma$  (PPAR $\gamma$ ) agonists
- Any other antidiabetic drug except those permitted in inclusion criterion #5 (metformin, sitagliptin, alogliptin, empagliflozin, canagliflozin, and dapagliflozin)
- Topiramate, amiodarone, bile salt chelators, methotrexate, equal or more than 800 U of vitamin E per day, chronic use (> 2 consecutive weeks) of corticosteroids with a systemic effect at doses  $\geq$ 10 mg/day of oral prednisone (or equivalent), orlistat, obeticholic acid or any other medications (including vitamins, herbal and dietary supplements) known to affect liver function/steatosis at the Investigator's discretion

31. Use of non-permitted medications related to the risk of drug-drug interaction at randomization visit.

#### Corporate confidential information

Those medications should be stopped or switched if the patient is eligible for randomization based on all other inclusion/exclusion criteria.

#### 32. Contraindications to MRI

- Such as patients with pacemakers, metallic cardiac valves, magnetic material such as surgical clips, implanted electronic infusion pumps or other conditions that would preclude proximity to a strong magnetic field
- History of extreme claustrophobia

- The patient cannot fit inside the magnetic resonance scanner cavity

33. Pregnancy or lactation

### 5.3 Rescreening

Re-screening is permitted once with the approval of the Medical Monitor and the POXEL Medical Representative if a subject has not met the eligibility criteria within the screening period with the following exception:

- If a subject fails screening due to Inclusion Criterion #7 in Section 5.1, re-screening is not permitted.

Patients are only allowed to be re-screened once; the entire screening process (including informed consent signature) must be repeated except MRI-PDFF only if the investigator can ensure that there will be maximum 10 weeks between MRI-PDFF and Randomization Visit (V1).

### 5.4 Retesting during the Screening Period

If the investigator is not able to assess patient's eligibility for any of the laboratory or imaging eligibility criteria in cases of technical malfunction (e.g. loss of laboratory specimen) or an indeterminate result (e.g. out of stability sample, breathing motion artifact during the MRI) should be retested.

If there is reason to believe the assessment result may be inconsistent (i.e. contradicts recent result for the same parameter), the test may be repeated once within the screening period only with the approval of the Medical Monitor and the POXEL Medical Representative. If the original result was exclusionary and is confirmed by repeat testing, then the patient is to be considered a screen failure; these subjects may be rescreened as described in Section 5.3.

### 5.5 Restrictions during the Study

Investigators will explain to the patients at Randomization Visit (V1) the AASLD guidance [6] regarding diet and exercise. Investigators will collect the compliance to this guidance at each subsequent visit. Patients must make every effort to maintain the same diet/exercise treatment through the study. They will be asked about their compliance to this guidance at every visit. Answers will be documented in source documents and reported in the electronic Case Report Form (eCRF).

Patients must be in a fasting condition for at least 10 hours (during which only water is permitted) prior to all study visits.

To respect *Inclusion criteria* #9, women of child-bearing potential must immediately contact the Investigator if they suspect they might be pregnant or if they have changed, or plan to change their birth control method.

Effective contraception (as detailed in the *Inclusion criterion #9*) or abstinence should be used during the study and for at least 7 days after the last dose of study drug for both males and females of child-bearing potential.

Patients should not donate blood or blood products, sperm or oocytes during the study.

Any modifications or deviations regarding these restrictions must be documented in the patient file.

## 5.6 Patients Incorrectly Randomized

Patients who fail to meet the inclusion/exclusion criteria must not, under any circumstances, enter the double-blind treatment period.

If a patient who does not meet the inclusion/exclusion criteria mistakenly enters the double-blind treatment period, a discussion should occur between the POXEL Medical Representative, the

Medical Monitor and the Investigator regarding whether to continue or discontinue the IMP, based on patient's safety and study's consideration. In situations where an agreement cannot be reached, the patient should be withdrawn from the study. In such case, patients will be considered as withdrawn from the study due to protocol deviation.

## 5.7 Criteria for Screen-failure

Patients who are withdrawn from the study between the Screening Period and the Randomization Visit (V1) will be considered as screen failure.

### Patients must be screen-failed in the event of any of the following:

1. Target LFC (MRI-PDFF) not met (as defined in Section 5.1 *Inclusion Criteria, Inclusion Criteria #6*)
2. Target liver histology criteria not met (as defined in Section 5.1 *Inclusion Criteria, Inclusion Criteria #7*)
3. Cap reached for patients with NASH CRN fibrosis F1 (see Section 4.1 *Study Design and Schedule*)
4. Other Inclusion criteria not met (as defined in Section 5.1 *Inclusion Criteria*)
5. Occurrence of an AE or SAE which is clinically relevant and affects patient's safety, if withdrawal from the study is considered necessary by the Investigator or POXEL Medical Representative
6. Occurrence of pregnancy
7. Important protocol deviation if withdrawal from the study is considered necessary by the Investigator or POXEL Medical Representative/designee

8. Intake of non-permitted drug (as defined in Section 6.5 *Non-permitted Medicines*) if withdrawal from the study is considered necessary by the Investigator or POXEL Medical Representative/designee
9. Occurrence of any other Exclusion criteria (as defined in Section 5.2 *Exclusion Criteria*)
10. Withdrawal of patient informed consent
11. Lost to follow-up

The reason for screen failure must be documented in source documents and reported in the eCRF and interactive web response system (IWRS). If more than one reason is given, the Investigator should make all efforts to establish the main reason.

The Investigator will verify AE and concomitant medications. This information will be recorded in the patient file and in the eCRF, including screen-failure reason and date.

Patients will then be referred to their physician for the pursuit of routine medical care.

## **5.8 Criteria for Withdrawal from the Study for Randomized Patients during the Double-blind Treatment Period**

### *5.8.1 Criteria for withdrawal from the study*

Patients may withdraw from the study at any time at their own request.

**The Investigator must temporarily interrupt or permanently discontinue the IMP if continued administration of the IMP is believed to be detrimental to the patient well-being.**

**IMP should be discontinued and the patient should be withdrawn from the study in the event of any of the following:**

1. Occurrence of an AE or SAE which is clinically relevant and affects patient's safety (Common Terminology Criteria for Adverse Events (CTCAE) grade 3 or higher AE related to the drug **OR** CTCAE grade 4 or higher regardless of attribution to the study drug), if discontinuation of the IMP is considered necessary by the Investigator or POXEL Medical Representative
2. Occurrence of pregnancy
3. Important protocol deviation if discontinuation of IMP is considered necessary by the Investigator or POXEL Medical Representative/designee
4. Intake of non-permitted drug (as defined in Section 6.5 *Non-permitted Medicines*) if discontinuation of IMP is considered necessary by the Investigator or POXEL Medical Representative/designee
5. Requirement of an emergency unblinding (as described in Section 6.3.3.2 *Emergency Unblinding*)
6. Withdrawal of patient informed consent

7. Lost to follow-up
8. Sponsor decision (as defined in Section 5.9 *Discontinuation of the Study*)

In case of temporary interruption of the IMP, the decision to resume the IMP should be taken in agreement by the Investigator, POXEL Medical Representative and Medical Monitor.

#### 5.8.2 *Procedure for withdrawal from the study*

**In the case of discontinuation of IMP for any reason listed in Section 5.8.1 *Criteria for withdrawal from the study* except SAE leading to death and lost to follow-up, patients will be asked to perform an Early Termination Visit within 8 days after the IMP discontinuation. At the Early Termination Visit, patients will be considered as withdrawn patients.** This visit will allow the Investigator to check the medical status of the patient and the patient to return all the IMP kits (used and unused), his/her patient diary and the self-monitoring blood glucose (SMBG) device for review if applicable. The SMBG device will be kept by the patient after the end of his/her study participation if applicable. The reason and date for withdrawal from the study must be documented in source documents, and reported in the eCRF and in the IWRS. If more than one reason of study withdrawal is given, the Investigator should make all efforts to establish the main reason.

If there is any medical reason for withdrawal from the study, the patient will remain under the supervision of the Investigator until resolution or stabilization of the medical condition. The Investigator must make every effort to collect the information related to the outcome of the event, as described in Section 8.3.8.5. This information is recorded in the part of eCRF dedicated to AEs. If the IMP is discontinued as a result of a SAE/AESI/Overdose/Pregnancy, the procedure described in Section 8.3.8.4 is to be implemented.

If patients are lost to follow-up, all reasonable means of contact must be used. In addition, a letter must be sent to the patient and a copy filed in the patient file (if allowed by site's Standard Operating Procedures). All the attempts (at least 3 by telephone by the Investigator or Clinical Research Coordinator (CRC) at study site) must be recorded in the patient file; last contact date will be reported in the eCRF.

Any withdrawal from the study, irrespective of the reason, is to be notified immediately to the Medical Monitor and POXEL Medical Representative.

## 5.9 Discontinuation of the Study

The whole study may be discontinued by POXEL in the event of any of the following:

- New information leading to unfavorable risk-benefit ratio of IMP, e.g. due to:

- Occurrence of significant previously unknown adverse reactions or unexpectedly high severity or incidence of known adverse reactions, or
- Other unfavorable safety findings
- POXEL's decision that continuation of the study is unjustifiable for medical or ethical reasons
- Poor enrollment of patients making completion of the study within an acceptable time frame unlikely
- Discontinuation of development of the POXEL's IMP

The study will be paused if any of the following occurs:

- Three patients develop the same Grade 3 CTCAE classified as related to study drug
- Two patients develop the same Grade 4 CTCAE classified as related to study drug
- One patient develops a grade 5 CTCAE classified as related to study drug

In case the study is paused, the Sponsor will organize an *ad hoc* global safety board according to Sponsor's Standard Operating Procedures. This global safety board will assess the benefit/risk ratio in order to decide whether the study should be stopped or can be continued. This assessment/conclusion will be sent to Competent Authorities.

Competent Authorities and Institutional Review Boards/Ethics Committees (IRB/EC) will be informed about the discontinuation of the study in accordance with applicable regulations.

The study may be terminated or suspended upon request of Competent Authorities.

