#### 8.3.8.1 Adverse Event Definitions

##### 8.3.8.1.1 Adverse Event (AE)

An AE is any untoward medical occurrence in a patient or clinical investigation patient administered a pharmaceutical product, which does not necessarily have a causal relationship with this treatment. An AE can therefore be any unfavorable and unintended sign (including an abnormal laboratory finding), symptom, or disease temporally associated with the use of a medicinal, whether or not considered related to the medicinal product.

The official definition also extends to AEs occurring under placebo or in a reference group receiving drug or non-drug therapy. Because of regulatory requirements, events occurring during drug-free and pre- and post-treatment periods should also be designated as AEs.

Therefore, safety surveillance applies to the time when the patient is included into the study (date of ICF signature) until the End-of-Study Visit (V9-EoS) performed two weeks after the End-of-Treatment Visit (V8-EoT).

In cases of surgical or diagnostic procedures, the condition/illness leading to such a procedure is considered as the AE rather than the procedure itself.

Adverse events will be assessed according to the Common Terminology Criteria for Adverse Events (CTCAE) version 5.0.

The Investigator is required to grade the severity/intensity of each AE according to CTCAE:

- CTCAE Grade 1: Mild; asymptomatic or mild symptoms; clinical or diagnostic observations only; intervention not indicated
- CTCAE Grade 2: Moderate; minimal, local or noninvasive intervention indicated; limiting age-appropriate instrumental activities of daily living (ADL)
- CTCAE Grade 3: Severe or medically significant but not immediately life-threatening; hospitalization or prolongation of hospitalization indicated; disabling; limiting self care ADL
- CTCAE Grade 4 (Life threatening): life-threatening consequences; urgent intervention indicated

- CTCAE Grade 5 (Death): death related to AE

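### The study-pause rule counts Grade 3 and Grade 4 cases separately, so the same related event at Grades 3, 3 and 4 forces no pause while 3, 3 and 3 does

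*Protocol*

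**What the plan says.** Protocol Section 5.9 contains two separate provisions.

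- **Mandatory pause.** The list opens with "The study will be paused if any of the following occurs" and gives three triggers. The first is "Three patients develop the same Grade 3 CTCAE classified as related to study drug". The second, one grade up and with a lower count, is "Two patients develop the same Grade 4 CTCAE classified as related to study drug". The third, for a fatal event, is "One patient develops a grade 5 CTCAE classified as related to study drug". If the study is paused, the sponsor convenes an ad hoc global safety board. The board weighs benefit against risk, decides whether the study continues, and its conclusion goes to the authorities.
- **Discretionary stop.** "The whole study may be discontinued by POXEL in the event of any of the following" introduces a list that includes unexpectedly severe or frequent reactions and other unfavourable safety findings.

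Section 5.8.1, on withdrawing an individual patient, uses cumulative wording. It refers to a "grade 3 or higher AE related to the drug", and to Grade 4 or higher whatever the attribution, in both cases if discontinuation is judged necessary.

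Section 8.3.8.1.1 fixes the severity order: "CTCAE Grade 3: Severe or medically significant but not immediately life-threatening", against "CTCAE Grade 4 (Life threatening): life-threatening consequences; urgent intervention indicated". The SAP contains no pause rule.

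**The concern.** A safety trigger should never respond less to a worse set of cases. Here it can. The Grade 3 trigger counts Grade 3 cases and the Grade 4 trigger counts Grade 4 cases, so a cluster split across the two grades can fall short of both. If one of three Grade 3 patients had instead had a life-threatening case, the mandatory pause would become no pause.

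In Section 5.9 the ad hoc board is convened only when the study is paused. No interim analysis is planned (Protocol Section 9.6, SAP Section 7.8), and the protocol text available for this review names no standing safety board. That text does not include Annex 1, the administrative structure. What is at stake is a delayed benefit/risk review, with further patients dosed in the meantime.

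**Working it through.** The protocol states no operating characteristic for the pause rule, so there is no figure of its own to reproduce. The check is a logical enumeration, followed by an illustration of size.

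**1. The rule as written.** Let n3, n4 and n5 be the numbers of patients whose case of one related event is Grade 3, 4 or 5. From Section 5.9:

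- Literal rule: pause if n3 ≥ 3, or n4 ≥ 2, or n5 ≥ 1.
- Cumulative ('or higher') rule, for comparison: pause if n3+n4+n5 ≥ 3, or n4+n5 ≥ 2, or n5 ≥ 1.

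**2. The two clusters.**

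| Grades of the three cases | n3 | n4 | Literal rule | Cumulative rule |
|---|---|---|---|---|
| 3, 3, 3 | 3 | 0 | pause | pause |
| 3, 3, 4 | 2 | 1 | no pause | pause |

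**3. How many patterns are affected.** Enumerating n3 from 0 to 5, n4 from 0 to 5 and n5 from 0 to 2, the two rules disagree in exactly one configuration: (n3, n4, n5) = (2, 1, 0). From there a fourth case gives (3, 1, 0), (2, 2, 0) or (2, 1, 1), each of which triggers the literal rule. The delay is therefore one further case of Grade 3 or above.

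**4. Size, given a cluster of three.** Suppose three patients have the same related event at Grade 3 or 4, and let q be the share of such cases that are Grade 4. The documents give no value for q, so a range is shown. The pause is missed when exactly one of the three is Grade 4:

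P(missed) = 3q(1 − q)²

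| q (assumed) | Calculation | P(missed) |
|---|---|---|
| 0.05 | 3 × 0.05 × 0.95² | 0.135 |
| 0.10 | 3 × 0.10 × 0.90² | 0.243 |
| 0.20 | 3 × 0.20 × 0.80² | 0.384 |
| 0.33 | 3 × 0.33 × 0.67² | 0.444 |

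**5. Size, unconditionally.** This uses exact trinomial probabilities for one event type with no Grade 5 cases. N is either all 120 randomised patients or the 90 planned on active drug (3 × 30). Per-patient rates are assumed.

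| N | Grade 3 rate | Grade 4 rate | P(pause), literal | P(pause), cumulative | Difference |
|---|---|---|---|---|---|
| 90 | 1% | 0.25% | 0.082 | 0.112 | 0.029 |
| 120 | 1% | 0.25% | 0.152 | 0.200 | 0.048 |
| 90 | 2% | 0.5% | 0.324 | 0.402 | 0.078 |
| 120 | 2% | 0.5% | 0.502 | 0.589 | 0.087 |
| 90 | 2% | 1% | 0.437 | 0.536 | 0.100 |
| 120 | 3% | 1% | 0.805 | 0.869 | 0.064 |

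Over all the rates tried (Grade 3 1–3%, Grade 4 0.25–1%), the difference runs from about 3 to 10 percentage points. It is the chance that the study ends in the (2, 1, 0) state without ever pausing. Studies that pass through that state and then see a fourth case pause late, and count as paused under both rules.

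**The case against.** **Another reading is possible.** The 3/2/1 ladder plainly intends higher grades to need fewer cases, and a patient who worsens to Grade 4 might be said to have developed the Grade 3 event on the way. Section 5.8.1 concerns one patient, where 'or higher' comes naturally, so its contrast with Section 5.9 is only modest evidence of intent. That is fair as to intent. But no text says that a Grade 4 case also counts as Grade 3. Section 8.3.8.3 records one severity grade per event, and the SAP's summaries by maximum severity (Section 7.7.2) count a patient once, under the worst grade. If the sponsor meant a cumulative count, the rule does not say so.

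**Other controls exist.** Life-threatening events are serious and reach the sponsor within 24 hours (Sections 8.3.8.1.3 and 8.3.8.4.1). Withdrawals are notified at once (Section 5.8.2). Liver injury has its own drug-stopping criteria (Section 8.3.8.1.4). Unexpected serious reactions go to the authorities, and the sponsor may stop the study. A 3, 3, 4 cluster would therefore not go unseen. None of these provisions, however, makes a pause or a board review mandatory for it.

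**The effect is narrow.** One pattern is affected, the delay is one patient, and the 14–44% is conditional on a cluster whose frequency the documents do not give. This stands, and it limits the weight of the point. No endpoint, estimate or error rate is touched.

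**It may be too late for this trial.** The planned study end was Q1 2022, and SAP version 3.0 is dated 12 August 2022, after the blinded data review meeting. If dosing is over, an amendment protects no one here. This also stands. It affects where the correction is useful, not whether the rule is sound.

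**Conclusion.** The concern holds. Followed literally, Section 5.9 requires a pause for three Grade 3 cases of the same related event and none when one of the three is Grade 4. This logical inversion does not depend on any assumed rate.

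Its practical reach is small: one configuration and a delay of one further case at Grade 3 or above. Given a cluster of three, the pause is missed in 14%, 24%, 38% or 44% at assumed Grade 4 shares of 5%, 10%, 20% or 33%. Unconditionally, for one event type at the assumed rates, closing the gap raises the chance of a pause by about 3 to 10 percentage points. Both ranges are illustrations, and the unconditional one treats patients as independent with common event rates. The rule should be corrected, but the point has no bearing on the efficacy analysis.

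**What to change.** Bring Section 5.9 into line with the wording already used in Section 5.8.1. Either make the first two triggers read Grade 3 or higher and Grade 4 or higher, or add a sentence saying how a higher-grade case enters the lower-grade count. The property to secure is that a more severe case never counts for less than a milder one. The grades and counts themselves remain for the sponsor's safety team to set.

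The cost is a few words in a protocol amendment and, in mixed-grade clusters, a pause that may come one patient earlier. If dosing in this trial has finished, the correction belongs in the protocol of the Phase 3 study that this trial is meant to inform (Section 4.2).
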